#### **12.3.3.4 Vital Sign Analyses**

Summary statistics of vital sign data at each time point will be calculated by treatment group, and the change at each time point from baseline will be graphically displayed.

#### **12.3.3.5 Electrocardiogram Analyses**

A frequency table of investigator-assessed 12-lead ECG data at each measurement point will be prepared.

#### **12.3.3.6 Analysis of Physical Findings**

Not applicable.

#### **12.3.3.7 Exploratory Safety Analyses**

Not applicable.

### **12.4 Proceeding to the Next Cohort**

#### **12.4.1 Procedures for Proceeding to the Next Cohort**

In each cohort, subjects will be evaluated one by one to confirm the absence of symptomatic intracranial hemorrhage through Visit 2 (36 hours after study drug administration) before enrolling the next subject, until 3 subjects aged  $\geq 81$  years are enrolled in the DS-1040b group. The next subject will then be enrolled. The next subject cannot be enrolled until the absence of symptomatic intracranial hemorrhage for 36 hours after study drug administration is confirmed.

Assessment for proceeding to the next cohort will be performed according to the procedures specified below. Study drug administration for the next cohort will be initiated immediately after the decision on proceeding to that cohort is made; it is not necessary to have a certain interval between the cohorts.

- 1) The investigator or subinvestigator will review the safety data after Visit 4 assessment, and immediately prepare the CRF.
- 2) The sponsor will obtain the data for safety data review. The central adjudication committee member will assess intracranial hemorrhage and (TIMI) major bleeding in a blinded fashion.

- 3) Based on the available information, the sponsor will discuss with the medical expert to determine whether the study should proceed to the next cohort in reference to Section 12.4.2 “Criteria for Discontinuation or Temporary Discontinuation of the Study.”

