### 3. STUDY DESIGN

#### 3.1 Overall Design

This study is a multicenter, single-blind, placebo-controlled, randomized, intergroup ascending dose study to confirm the safety and tolerability of DS-1040b in patients with acute ischemic stroke in whom a thrombectomy device is indicated. There will be a total of 4 cohorts, with a planned sample size of 54 or 60 subjects (6 or 12 subjects in the 0.6 mg cohort and 16 subjects per cohort in the other cohorts). The 0.6 mg cohort will only consist of a DS-1040b group. In the other cohorts, subjects will be randomized to the DS-1040b or placebo group in a 3:1 ratio. If any one of the first 6 subjects in the 0.6 mg cohort experiences one event defined as one requiring, “necessary actions to be taken, including discontinuation of the study” as specified in Section 12.4.2, an additional 6 subjects will be enrolled to confirm the safety in a total of 12 subjects. In each cohort, subjects will be evaluated one by one to confirm the absence of symptomatic intracranial hemorrhage through Visit 2 (36 hours after study drug administration) before enrolling the next subject, until 3 subjects aged  $\geq 81$  years are enrolled in the DS-1040b group. In each cohort, safety evaluation will be performed when all data collected through Visit 4 (96 hours after study drug administration) are available to determine whether the study should proceed to the next cohort. Subjects will be required to receive inpatient treatment until Visit 4 at the earliest.

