### **5.1.2 Method of Randomization**

The independent biostatistician will prepare a randomization schedule as instructed by the sponsor. In Cohorts 2 to 4, subjects will be randomized to the DS-1040b or placebo group in a 3:1 ratio using block randomization. The study drug with the same drug number will be used exclusively for one subject and will not be used for any other subjects.

Subjects will be enrolled in the study via the web-based interactive response technology (IRT) system. The procedures for subject enrollment are shown in Figure 5.1-1.

After obtaining written informed consent from each subject (or his/her legally acceptable representative), the investigator or subinvestigator will prepare the subject screening list and assess the subject's eligibility.

The investigator, subinvestigator, or study staff will enter the required information of subjects from whom informed consent has been obtained into the IRT system. A study-specific subject number will be assigned by the IRT system. The investigator, subinvestigator, or study staff will then enter the subject's eligibility assessment result into the IRT system. Via the IRT system, randomization of subjects assessed as eligible

[figure not shown]
will be performed. If the subject is randomized to the DS-1040b group, a drug number will be notified by the IRT system. If the subject is randomized to the placebo group, the term “placebo” will be displayed.

Based on the results of randomization on the IRT system, DS-1040b or placebo with a drug number displayed on the system should be prepared at the required dose to start study drug administration. The date of randomization will be defined as the date of enrollment.

The investigator or subinvestigator will explain the reason for ineligibility to each subject assessed as ineligible by the investigator or subinvestigator, and initiate alternative treatment. The investigator or subinvestigator will also record the reason for not enrolling the subject in the subject screening list.

If study drug administration cannot be started after randomization due to, for example, a sudden change in the health condition of the subject, the date of and reason for dropout will be recorded in the case report form (CRF).

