**Figure 5.1-1 Procedures for Subject Enrollment in Each Cohort**

### 5.1.3 Blinding

This study will be conducted as a single-blind study, in which subjects will be blinded.

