## **6.15 Laboratory Tests**

The parameters listed below will be measured before and at 6 hours after the start of study drug administration, at Visits 2 and 4, and at the time of discontinuation, and the presence or absence of measurements, the date/time of blood collection, and the measurement results will be recorded in the CRF. Each study center’s reference ranges will be used for laboratory data.

- Hematology test: red blood cell count, hemoglobin, hematocrit, white blood cell count, white blood cell differential (neutrophil, lymphocyte, monocyte, eosinophil, basophil), platelet count
- Blood chemistry test: total protein, albumin, A/G ratio, total bilirubin, direct bilirubin, AST, ALT, ALP,  $\gamma$ -GT, LDH, CK, BUN, creatinine, uric acid, Na, K, Cl, Ca, P, Mg, total cholesterol, triglyceride, glucose, CRP

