#### **10.4.8 Assessment of Bleeding Adverse Events**

The investigator or subinvestigator will determine whether each AE is a bleeding event, and will record it, with the presence or absence of external factors (with details, if present), in the CRF.

- In case of intracranial hemorrhage

The type of intracranial hemorrhage (symptomatic or asymptomatic), the date/time of the NIHSS assessment (at baseline and onset), and the details of the event will be recorded in the CRF.

- In case of non-intracranial hemorrhage

The presence or absence of a 5 g/dL or greater decrease in hemoglobin, the presence or absence of blood transfusion (with the date/time, name, amount of blood transfusion, and AE(s) requiring blood transfusion, if present), the presence or absence of surgical treatment (with details, if present), and the details of the event will be recorded in the CRF.

The final classification and assessment of bleeding events will be performed by the central adjudication committee member in a blinded fashion. The investigator or

subinvestigator will provide the sponsor with head imaging results used as the basis for assessment.

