#### **12.3.3.2 Adverse Event Analyses**

The incidence of treatment-emergent adverse events (TEAEs) will be calculated by treatment group, and the frequency of each TEAE will be tabulated by event and by severity. Similar analyses will be performed for treatment-related and bleeding TEAEs.

A TEAE is defined as an AE that is not present prior to the study and occurs after the start of study drug administration but before Visit 5 (Day 30), or an AE that worsens in severity after the start of study drug administration but before Visit 5 (Day 30).

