## 13.3 Data Management

Each subject will be identified in the database by a unique subject number as defined by the sponsor.

To ensure the quality of clinical data across all subjects and study centers, subject data will be reviewed according to the specifications given to the sponsor. Data will be vetted both electronically and manually for CRFs and subject data will be checked for consistency, completeness and any apparent discrepancies. CRF data will be electronically vetted by programmed data rules within the application. Queries generated by rules and raised by reviewers will be generated as queries within the EDC application.

Data received from external sources such as the central laboratory will be reconciled to the clinical database in accordance with the data management plan.

SAEs in the clinical database will be reconciled to the safety database.

All AEs will be coded using Medical Dictionary for Regulatory Activities (MedDRA).

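### The only described route by which a non-intracranial bleed reaches the blinded adjudicator starts with an investigator who knows the allocation, so adjudication does not fully protect TIMI major bleeding from assessment bias

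*Combined protocol and SAP*

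**What the plan says.** Only the subject is blinded. Section 5.1.3 states: "This study will be conducted as a single-blind study, in which subjects will be blinded". The site learns the allocation at randomization: "If the subject is randomized to the DS-1040b group, a drug number will be notified by the IRT system" (5.1.2), and the system displays the word placebo otherwise. In the lowest cohort nothing is concealed: "The 0.6 mg cohort will only consist of a DS-1040b group" (3.1).

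Section 3.2 accepts that this could bias assessment and answers that a blinded central adjudicator will assess both types of intracranial hemorrhage and TIMI major bleeding. Step 2 of 12.4.1 repeats it for the escalation decision: "The central adjudication committee member will assess intracranial hemorrhage and (TIMI) major bleeding in a blinded fashion".

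Section 10.4.8 describes what comes before the adjudicator: "The investigator or subinvestigator will determine whether each AE is a bleeding event, and will record it". For a non-intracranial hemorrhage the site then fills in dedicated fields for the hemoglobin fall, transfusion and surgical treatment, and the adjudicator makes the final classification of bleeding events. Section 10.4.1 adds a second question on every AE, whether it involved obvious bleeding, which is also answered by the site.

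Three outputs depend on this chain or may do so: the primary endpoint of TIMI major bleeding within 96 hours (7 and 12.3.3.1), the 12.4.2 criterion under which one such event in the DS-1040b group of a cohort pauses enrollment, and the bleeding AE table, for which 12.3.3.2 says only: "Similar analyses will be performed for treatment-related and bleeding TEAEs".

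**The concern.** Blinded adjudication protects the step at which a case is classified. It protects the step at which a case is found only if finding does not depend on someone who knows the treatment. For non-intracranial bleeding the finding step, as written, is a judgment by unblinded site staff. An event entered as anemia, as a hemoglobin decrease or as a puncture-site complication, without a bleeding flag, has no stated path to the adjudicator.

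The filter works one way. The adjudicator can reject a flagged event that does not qualify, and can upgrade a flagged bleed that was under-graded. Recovering an unflagged bleed is not provided for.

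Flagging could go either way in a trial of a profibrinolytic drug. A site may flag more readily on active drug, or may more readily put a bleed down to the thrombectomy procedure. What is at stake is a primary safety endpoint and a criterion that acts on a single event, in a study with no data monitoring committee (12.4.4, 16.10).

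**Working it through.** **Step 1. The two primary bleeding endpoints side by side.**

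| | Intracranial hemorrhage | Non-intracranial TIMI major bleeding |
|---|---|---|
| Scheduled test in every subject | Head imaging at 24 to 36 hours (6.3, 6.13) | Hemoglobin, measured "before and at 6 hours after the start of study drug administration, at Visits 2 and 4" (6.15) |
| Sent to the adjudicator regardless of the site's opinion | Yes, images are submitted for central classification (6.13) | Not stated |
| Described entry to adjudication | Scheduled images, plus AE flag | AE flag by the site (10.4.8) |
| Classification | Blinded | Blinded |

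The difference is in the second row. The hemoglobin values exist, but no section links a fall to referral.

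**Step 2. What is captured without the bleeding flag.** Hemoglobin is in the CRF for all subjects at four scheduled times (6.15). Drug and non-drug interventions for any AE are recorded at each visit (6.2 to 6.5, 6.7). AE terms are coded in MedDRA (13.3). Only the dedicated bleeding fields of 10.4.8 depend on the flag. Transfusion is asked for by name only there.

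**Step 3. Why transfusion matters to the definition.** Section 7 counts 2 transfused units as 1 g/dL, so corrected fall = observed fall + units/2. An observed fall of 4 g/dL with 2 units gives 4 + 2/2 = 5 g/dL, which reaches the threshold although the laboratory series alone shows 4.

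**Step 4. Group sizes.** From 12.5: 6 + 3 × 16 = 54 and 12 + 3 × 16 = 60, as stated; 16 at 3:1 gives 12 DS-1040b and 4 placebo.

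**Step 5. Effect of one unflagged event.** Section 12.3.3.1 asks for a point estimate and a 95% interval without naming a method; exact Clopper-Pearson intervals are used here.

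- 12 DS-1040b subjects: 1/12 = 8.3% (0.2 to 38.5) becomes 0/12 = 0% (0 to 26.5).
- 6 DS-1040b subjects (first stage of the 0.6 mg cohort): 1/6 = 16.7% (0.4 to 64.1) becomes 0/6 = 0% (0 to 45.9).

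In both cases the TIMI pause criterion goes from met to not met. In the 0.6 mg cohort, 3.1 makes the expansion from 6 to 12 subjects depend on the same list of criteria, so that trigger would be lost too unless another criterion was met.

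**Step 6. Illustration only.** The documents give neither a true TIMI major bleeding rate p nor the share s of true bleeds that sites flag. With n = 12, the probability that the criterion triggers is 1 − (1 − p·s)^12. At an assumed p = 5%:

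- s = 1: 1 − 0.95^12 = 46.0%
- s = 0.75: 1 − 0.9625^12 = 36.8%
- s = 0.5: 1 − 0.975^12 = 26.2%

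At s = 0.75 the corresponding change is from 21.5% to 16.6% for p = 2%, and from 71.8% to 60.8% for p = 10%. These figures show how the criterion responds to missed flags. They are not estimates for this trial, and an s of 0.5 or 0.75 is hard to believe for an overt bleed of this size.

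**The case against.** The best case for the plan is that the missed event would have to be unusual. TIMI major bleeding requires a clinically evident bleed with a fall of at least 5 g/dL. To escape, such a bleed would have to be recorded as something else despite scheduled hemoglobin, investigator appraisal of all laboratory results (10.1), probable SAE reporting within 24 hours with a narrative (10.5), and sponsor review with a medical expert before escalation (12.4.1). This argument stands, and it limits the likely size for this endpoint.

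Four stronger readings are tempting, and the documents do not support them.

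- A reader might infer that hemoglobin and treatment details are recorded only for flagged bleeds. Step 2 of the working shows otherwise.
- A reader might infer that an unflagged event can never reach the adjudicator. No section lists what the adjudicator receives, the Central Adjudication Form named in 13.2.2 is not in the text reviewed, and a separate procedure could contain a trigger. The supportable statement is that no other route is described.
- A reader might infer that a missed TIMI event always means no pause. Treatment-related SAEs are a separate criterion in 12.4.2, although they rest on the same investigator's causality judgment (10.4.4). Nor can a difference in flagging between arms affect the pause rule, which counts DS-1040b subjects only; what matters there is under-flagging on active drug.
- A reader might infer that unflagged events are absent from the bleeding TEAE table, or that the table is biased by a definite amount. Section 12.3.3.2 does not say which bleeding status it uses, 12.1 and 12.6 leave detailed definitions to a separate SAP, and no labelling rates are given from which a bias could be computed.

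It is also fair to say that the study tests no hypothesis (2.2), so there is no type I error to inflate.

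**Conclusion.** The point holds as a gap in case-finding. For non-intracranial bleeding, the described path to blinded adjudication begins with a judgment made in knowledge of the allocation, and there is no feed independent of the site's flag like the one the protocol gives intracranial hemorrhage. The claim in 3.2 is therefore not fully supported for TIMI major bleeding.

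The direction of any bias is not determined by the documents. Its size is probably small for TIMI major bleeding and cannot be estimated from the text. The consequence of a single miss is nevertheless discrete: in a 12-subject arm the reported rate drops from 8.3% to 0% and the TIMI pause criterion is not met. For bleeding TEAEs the finding is narrower: the source of the bleeding status is undefined in the text reviewed.

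This rests on two assumptions: that no unpublished adjudication procedure already contains a label-independent trigger, and that 10.4.8 describes actual practice. If such a procedure exists, citing it in 10.4.8 would settle the referral part.

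**What to change.** In 10.4.8 and step 2 of 12.4.1, keep the investigator's flag and add a programmed listing, applied identically to every subject, that refers to the blinded adjudicator:

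- (a) any transfusion-corrected hemoglobin fall from predose of 5 g/dL or more through Visit 4, using the protocol's own threshold and conversion;
- (b) any recorded transfusion, with the CRF capturing transfusion for every subject and not only under a bleeding entry;
- (c) any AE whose MedDRA term is on a prespecified hemorrhage or anemia list.

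These are referral triggers. The adjudicator still decides whether the endpoint definition is met.

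In 12.3.3.2, define bleeding TEAEs from the prespecified MedDRA hemorrhage list plus adjudicated events, with the investigator's flag as a supplement. In 3.2, limit the claim about avoided bias to match.

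This reduces dependence on the investigator but does not remove it, since AE terms and the evidence that a bleed was clinically evident still come from site records. The cost is one listing per cohort review, a transfusion field in the CRF if it is not already there for all subjects, and wording in the protocol and SAP. The downside is a few extra cases for the same adjudicator that turn out not to be bleeds. The laboratory data and MedDRA coding are already planned, and no dose or stopping threshold changes.

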#### **12.4.2 Criteria for Discontinuation or Temporary Discontinuation of the Study**

If any of the criteria specified below are met, the study will be discontinued or temporarily discontinued. Similarly, the study may be discontinued or temporarily discontinued according to these criteria until 3 subjects aged  $\geq 81$  years are enrolled in the DS-1040b group in each cohort.

- 1) If the criterion below is met, the study will be discontinued at that point. After the decision on discontinuation is made, the sponsor will discontinue the study according to the procedures described in Section 16.9:
  - Occurrence of two events of symptomatic intracranial hemorrhage (intracranial hemorrhage with clinical deterioration causing an increase in the NIISS score of  $\geq 4$  points [defined by ECASS]) not attributable to external factors at 36 hours after the start of DS-1040b administration in the DS-1040b group in one cohort
- 2) To ensure the safety of subjects, subject enrollment will be temporarily discontinued and the necessary actions to be taken, including discontinuation of the study, will be considered if any of the criteria listed below are met. If the study is continued based on the results of consideration, subject enrollment will be resumed. If the study is discontinued, the sponsor will discontinue the study according to the procedures described in Section 16.9:
  - Occurrence of one event of symptomatic intracranial hemorrhage (intracranial hemorrhage with clinical deterioration causing an increase in the NIHSS score of  $\geq 4$  points [defined by ECASS]) not attributable to external factors at 96 hours after the start of study drug administration (Visit 4) in the DS-1040b group in one cohort
  - Occurrence of one event of non-intracranial (TIMI) major bleeding at 96 hours after the start of study drug administration (Visit 4) in the DS-1040b group in one cohort
  - Occurrence of any events requiring the consideration of study discontinuation, such as severe hepatic impairment (eg, total bilirubin  $\geq 10$  mg/dL, AST or ALT  $\geq 500$  IU/L, ALP of 5 times the study center’s reference range, bleeding tendency, symptoms of hepatic failure, including consciousness disorder [fulminant hepatitis], hepatic cirrhosis, hepatic tumor, jaundice persisting for

$\geq$  6 months), severe renal impairment (BUN  $\geq$  40 mg/dL, creatinine  $\geq$  4 mg/dL, urine protein  $>$  3+, macroscopic hematuria, blood clots, serum potassium  $\geq$  5.5 mEq/L), and treatment-related SAEs

The investigator or subinvestigator will retain the original copies of all source documents supportive of information recorded in the CRF. These original copies should be available at any time for review.

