**Figure 3.1-1 Flow of Study Procedures Prior to Study Drug Administration and Major Endpoints**

### 3.2 Discussion of Study Design

Randomization will be performed to avoid an imbalance between the placebo and DS-1040b groups. The study will be conducted as a single-blind, intergroup ascending dose study using 4 doses. Assessment bias potentially caused by single-blindness will be avoided by the involvement of a central adjudication committee member who will assess the primary endpoints of symptomatic and asymptomatic intracranial hemorrhage and (TIMI) major bleeding in a blinded fashion. With regard to proceeding to the next cohort, it is considered that the safety of subjects can be ensured by escalating the dose according to the criteria specified in Section 12.4 “Proceeding to the Next Cohort.”

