#### **<Rationale>**

The sample size in each cohort (6 or 12 subjects in each DS-1040b group) and the study discontinuation criterion (occurrence of two events of symptomatic intracranial hemorrhage [defined by ECASS] in the DS-1040b group in one cohort) were selected in reference to Study DS1040-A-U103, which is ongoing in Europe and the United States, to confirm the safety and tolerability of DS-1040b monotherapy in patients with acute ischemic stroke. The sample size for Study DS1040-A-U103 was determined based on the results of clinical studies of rt-PA therapy. Based on the 16% incidence of symptomatic intracranial hemorrhage in these clinical studies of rt-PA therapy, a sample size that allows the assessment of an incidence of symptomatic intracranial hemorrhage of  $\leq$  16% (16 subjects per cohort) and the criterion for proceeding to the next cohort (occurrence of two events of symptomatic intracranial hemorrhage [defined by ECASS] in the DS-1040b group in one cohort) were selected in Study DS1040-A-U103.

In the 0.6 mg cohort, the safety in 6 or 12 subjects in the DS-1040b group will be confirmed. If DS-1040b at this dose is shown to be safe, the study will proceed to the next cohort.

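### The sICH stop and pause both exempt bleeds put down to external factors, a term the plan does not define or assign to anyone to decide

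*Combined protocol and SAP*

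**What the plan says.** Section 12.4.2 sets two criteria based on sICH in the DS-1040b group of a cohort, and the synopsis repeats them. Two events end the study, counting only those "not attributable to external factors at 36 hours after the start of DS-1040b administration in the DS-1040b group in one cohort". One event leads to a temporary halt of enrollment and a review, counting only those "not attributable to external factors at 96 hours after the start of study drug administration (Visit 4) in the DS-1040b group in one cohort". The next bullet, one TIMI major bleed outside the skull, has no such exemption. Section 3.1 ties the expansion of the 0.6 mg cohort from 6 to 12 subjects to the same pause criteria.

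On who handles external factors, Section 10.4.8 has the investigator or subinvestigator judge whether an adverse event is a bleed; that person "will record it, with the presence or absence of external factors (with details, if present), in the CRF". On blinding, Section 5.1.3 reads: "This study will be conducted as a single-blind study, in which subjects will be blinded". Under Section 5.1.2 the allocation system shows the site either a drug number or the word placebo.

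The plan's answer to the open design is in Section 3.2: "Assessment bias potentially caused by single-blindness will be avoided by the involvement of a central adjudication committee member who will assess the primary endpoints". Section 12.4.1 describes the task at escalation: "The central adjudication committee member will assess intracranial hemorrhage and (TIMI) major bleeding in a blinded fashion". Section 10.4.8 also gives the adjudicator the final classification and assessment of bleeding events. Under Section 12.4.1 the sponsor, with the medical expert, decides whether to go to the next dose.

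**The concern.** Inclusion criterion 4 puts every subject through stent-retriever treatment, and Section 5.6.3 allows heparin during it. A procedural contribution could be argued for many intracranial bleeds in this population. If the procedure may count as an external factor, the exemption could cover a large share of the events the two criteria are meant to catch. The study referred to for the cohort size and stopping criterion, U103, excludes patients in whom thrombectomy is indicated (Section 1.2.2), so it does not settle the question.

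These are not bleeds the trial can set aside. Section 1.2.2 says the purpose is to confirm safety in combination with the device. The rationale to Section 4.2 accepts that DS-1040b might worsen existing bleeding. A procedural bleed that becomes symptomatic because of the drug is an event of direct interest.

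What is at stake is dose escalation. A cohort could have two sICH on DS-1040b, meet neither sICH criterion, and be followed by a doubled dose. The primary analysis (Sections 7 and 12.3.3.1) counts every sICH, so the report could then show 2/12 (16.7%, exact 95% CI 2.1% to 48.4%) at a dose the criteria let through. At 0.6 mg, one sICH labelled external among six subjects (16.7%, exact 95% CI 0.4% to 64.1%) would not by itself trigger the expansion. There is no data monitoring committee (Sections 12.4.4 and 16.10).

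**Working it through.** **Text check.** Three things are missing from the text provided: a definition of external factors, a statement on whether thrombectomy is one, and a named decision-maker. In the synopsis, the asterisk that gives final assessment to the blinded adjudicator follows the words for ECASS-defined sICH and comes before the external-factor clause. It covers whether the event is an sICH, not what caused it.

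**Inputs.**
- DS-1040b subjects per cohort in Cohorts 2 to 4: 16 × 3/4 = 12 (Section 12.5). The plan's totals reproduce: 6 + 3 × 16 = 54 and 12 + 3 × 16 = 60.
- Reference sICH rate behind the criterion: p = 16% (Section 12.5).
- Background rates cited for endovascular treatment alone: 3.1% and 4.9% (Section 1.2.2).
- Share of sICH labelled external, f: not in the documents, so assumed over a range.

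The plan gives no stopping probability, so there is none to reproduce.

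**Formulas.** The counted rate is q = p(1 − f). With n = 12:
- P(sICH pause) = 1 − (1 − q)^12
- P(stop) = 1 − (1 − q)^12 − 12q(1 − q)^11

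At p = 0.16 and f = 0: P(stop) = 1 − 0.1234 − 0.2821 = 0.5945. At f = 0.5, q = 0.08: P(stop) = 1 − 0.3677 − 0.3837 = 0.2487 before rounding of the terms.

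| Assumed f | P(stop), p = 16% | P(sICH pause), p = 16% |
|---|---|---|
| 0 (all count) | 59.5% | 87.7% |
| 10% | 53.3% | 84.5% |
| 25% | 43.1% | 78.4% |
| 50% | 24.9% | 63.2% |
| 75% | 8.1% | 38.7% |
| 100% | 0% | 0% |

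**At twice the cited background rates** (6.2% to 9.8%), P(stop) is 16.8% to 33.2% if all sICH count, and 5.2% to 11.4% at f = 50%.

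**Given exactly two sICH in a cohort**, the stop is met with probability (1 − f)² and neither sICH criterion is met with probability f². At f = 10%, 25%, 50% and 75%, the stop is met in 81%, 56%, 25% and 6%, and neither is met in 1%, 6%, 25% and 56%.

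**Price of counting everything, if the drug adds no risk** (3.1% to 4.9%):
- A 12-subject cohort has at least one sICH in 31% to 45%. If half were exempted this would be 17% to 26%.
- The first six subjects at 0.6 mg include at least one sICH in 17% to 26%.
- A 12-subject cohort has two or more in 5% to 11%. Over the whole trial (0.6 mg with 6 subjects, plus 6 more if exactly one event, then three cohorts of 12), 18% to 37% of trials would meet the two-event stop somewhere.

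**The case against.** Four points on the other side carry weight.

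**Section 12.5 is not a second rule.** A reader might infer a contradiction, because the sample-size rationale says "the study discontinuation criterion (occurrence of two events of symptomatic intracranial hemorrhage [defined by ECASS] in the DS-1040b group in one cohort) were selected" with no exemption. That passage also leaves out the 36-hour window, so it is shorthand. Sections 3.1 and 12.4.1 send the reader to 12.4.2 for the rule that operates.

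**The investigator's entry is not said to be decisive.** A reader might infer that someone who knows the arm settles the attribution. The documents say only that the investigator records it. The sponsor and medical expert decide on escalation, and the adjudicator's final assessment of bleeding events could be stretched to include cause. What stands is that no text says who decides.

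**The other safeguards are not all discretionary.** A treatment-related serious adverse event is itself a pause criterion in 12.4.2. Under Section 10.4.4 an event predicted by known pharmacology can be called related, and bleeding on a profibrinolytic drug may qualify. But the same section allows not related when other factors reasonably explain the event, and the unblinded investigator makes that call, so a bleed labelled external would tend to be called unrelated too. The one-by-one enrollment check in 12.4.1 has no exemption and may cover much of a cohort, but it ends once three DS-1040b subjects aged 81 or over are enrolled. The open-ended any-events item does rest on discretion.

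**Exempting a clearly procedural bleed from a hard stop is defensible.** Ending 18% to 37% of trials of a drug with no effect on bleeding is a real cost. This stands, and the fix leaves that exemption in place.

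The heading of 12.4.3 has no text in this copy, and the separate SAP and the Central Adjudication Form were not available. Any of them could define the term or name the assessor.

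**Conclusion.** The point holds as a gap in the two sICH criteria: an undefined exemption, with no stated decision-maker and only an unblinded recorder, in a trial where every subject undergoes a procedure that might be called external. The size depends on the assumed share. At a true 16% and 12 treated, a share of 10% costs about 6 percentage points of stopping probability (59.5% to 53.3%), and a share of 50% costs about 35 (59.5% to 24.9%). The documents give no basis for choosing within that range, and they do not support the extreme reading that thrombectomy exempts every sICH. They only fail to rule it out.

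The figures assume independent events and labels, a full cohort, all sICH within 36 hours, and comparable sICH definitions across the cited rates. They leave out the other pause triggers and the one-by-one check, so they describe the two sICH criteria alone and overstate the loss of protection overall. The primary endpoint analysis is unaffected. This is a cheap improvement to subject safety and to freedom from bias in escalation.

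**What to change.** 1. **Pause.** Delete the external-factor clause from the one-event sICH criterion in 12.4.2 and the synopsis. Every sICH in a DS-1040b subject within 96 hours then pauses enrollment for review and, at 0.6 mg, triggers the expansion to 12. Attribution is weighed in that review. The TIMI bullet already works this way.
2. **Stop.** Keep the exemption for the two-event criterion. State that thrombectomy, its complications and the drugs given for it are not by themselves external factors, and have the existing central adjudicator, blinded to arm, decide attribution. In the 0.6 mg cohort everyone receives DS-1040b, so blinding to arm adds protection only from Cohort 2 upward; at 0.6 mg the definition and change 1 do the work.

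Aligning the shorthand in 12.5 with 12.4.2 is optional.

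The cost is more pauses for review when the drug has no effect, at the rates shown in the working. No new procedure is needed, and the six extra subjects at 0.6 mg are already within the planned maximum of 60. The adjudicator gains one further judgement per sICH.
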